Study Protocol Summary

Title: Plantar Heel Pain: Multisegment Foot Motion and Muscle Function, FFI Translation, and Evaluation of Treatments

ClinicalTrials.gov ID: NCT03161314

Date of the document: 30 December 2016 (Ethic approval date)

Study 1: Comparative Study of Gait and Foot Segment Motion Between Individuals with Plantar Fasciitis and Healthy Controls

Study Protocol

This study was designed to compare multisegment foot motion and gait between individuals with PF and healthy controls. All participants were fully informed about the study and gave their consent before participating in the study. The researchers recruited adults aged 20 to 80 years. Participants included people who had been experiencing foot pain related to PF for at least one month and showed tenderness in specific areas of the foot. Those with other serious health issues, such as arthritis or neurological problems, or with severe pain preventing walking, were excluded. The healthy control group included people without any foot pain or history of PF. The two groups were matched by age, gender, height, and weight to ensure fair comparisons.

Each participant had reflective markers attached to specific points on their pelvis, legs, and feet. Using a sophisticated motion capture system and force plates, researchers recorded how their feet and legs moved while standing still and walking at a comfortable pace along an 8-meter walkway. Multiple walking trials were recorded, and the two successive trials, with gait speed similar to the controls, were selected for detailed analysis. The data were processed to remove noise and standardized over the gait cycle, allowing for meaningful comparisons between participants.

Statistical Analysis Plan

To analyze the data, the researchers first checked whether the measurements followed a normal distribution. They then compared the demographics between PF and healthy controls to confirm that the groups were well matched. After that, the main analysis investigated how foot movements and gait differed among three categories: the symptomatic side of individuals with PF, the asymptomatic side of individuals with PF, and healthy controls. This comparison was done using ANOVA, which can detect whether any group differed significantly from the others. A p-value of less than 0.05 was considered statistically significant, meaning the observed differences were unlikely due to chance.

Study 2: Translation and Validation of the Thai Version of the Foot Function Index (FFI-Th)

Study Protocol

This study employed a cross-sectional design to adapt and validate the Foot Function Index (FFI) into Thai (FFI-Th). The translation process followed internationally recommended cross-cultural adaptation guidelines. Initially, two bilingual translators independently performed forward translations from English to Thai, which were then synthesized by an expert committee into a single version. This was back-translated into English by two native English speakers fluent in Thai to check for consistency. The pre-final Thai version was harmonized through consensus among health professionals, followed by cognitive interviews with 20 individuals to ensure clarity and cultural relevance. The final version was proofread by a linguist before use.

Participants included adults who could read and understand Thai and reported foot problems. A minimum sample size of 48 participants was determined based on prior reliability studies of similar FFI versions. Data were collected using the FFI-Th questionnaire, along with the EQ-5D-5L (a quality of life measure) and a pain visual analogue scale (pain-VAS).

Statistical Analysis Plan

Data analysis was conducted using SPSS software with significance set at $p < 0.05$. Descriptive statistics summarized demographic characteristics and questionnaire scores. The study examined floor and ceiling effects to identify items with extreme response patterns and noted the frequency of “not applicable” responses.

The reliability of the FFI-Th was assessed: internal consistency was evaluated using Cronbach's alpha, with values above 0.7 indicating acceptable consistency. Test-retest reliability was measured by the intraclass correlation coefficient (ICC) from repeated assessments one week apart, with ICC values interpreted as poor (<0.5), moderate (0.5–0.75), good (0.75–0.9), or excellent (>0.9).

Construct validity was explored through Principal Component Analysis (PCA) using varimax rotation, retaining factors with eigenvalues greater than 1 to confirm the underlying questionnaire structure. Criterion validity was assessed by correlating the FFI-Th scores with both the pain-VAS and EQ-5D-5L using Pearson's correlation coefficient. Correlation strengths were interpreted as weak (<0.3), moderate (0.3–0.5), or strong (>0.5), with positive or negative values indicating the direction of the relationship.

Study 3: Effects of Strengthening and Stretching Exercise Programs on Pain and Gait in Patients with Plantar Fasciitis: A Randomized Controlled Trial

Study Protocol

This study was a double-blind randomized controlled trial conducted at Physical Therapy Center, Mahidol University. It aimed to compare the effects of strengthening versus stretching exercises on individuals with PF.

Participants were diagnosed with PF based on clinical symptoms and ultrasound measurement, and then were randomly allocated into two groups: strengthening and stretching. Both groups initially received standardized conservative physical therapy (therapeutic ultrasound and manual therapy) twice a week for 4 weeks. Subsequently, they followed their assigned home-based exercise program three days a week for 4 weeks, continuing independently for 2 months after supervised intervention ended. Participants and the physical therapist who provided a conservative PT intervention were blinded to group allocation.

Outcome assessments, including pain intensity via visual analog scale (VAS) and gait parameters measured on a force distribution platform, were performed at five time points: Baseline, 2 weeks after the intervention, 4 weeks after the intervention, 1-month follow-up, 2-month follow-up

Statistical Analysis Plan

Data distribution was tested for normality using the Kolmogorov-Smirnov test. Outcome measures were analyzed using two-way repeated measures ANOVA to examine:

- Main effects of time (changes across assessment points),
- Main effects of group (differences between strengthening and stretching groups),
- Interaction effects (whether changes over time differed by group).

Post-hoc Bonferroni tests identified specific time points with significant differences. Independent sample t-tests compared groups at individual assessment times. Statistical significance was set at $p < 0.05$. SPSS software was used for all analyses.

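### Study 1 matches on age, gender, height and weight, but its ANOVA names no term for them; so far as they predict the outcome, the symptomatic-side-versus-control test loses power

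*Combined protocol and SAP*

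**What the plan says.** The Study Protocol part of Study 1 states that "The two groups were matched by age, gender, height, and weight to ensure fair comparisons". It does not say whether controls were paired to individual patients or the groups were balanced as a whole, and it gives no ratio or tolerance. It adds that "the two successive trials, with gait speed similar to the controls, were selected for detailed analysis", without saying whether the two trials are averaged.

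The Statistical Analysis Plan part of Study 1 uses the matching variables once, as a balance check: "They then compared the demographics between PF and healthy controls to confirm that the groups were well matched". The main comparison is among "the symptomatic side of individuals with PF, the asymptomatic side of individuals with PF, and healthy controls", and the method is given in one sentence: "This comparison was done using ANOVA, which can detect whether any group differed significantly from the others". The threshold is 0.05 ("A p-value of less than 0.05 was considered statistically significant"). No covariate, matched-set, participant or trial term is named. Study 1 states no sample size, SD, target difference or correlation; the minimum of 48 participants belongs to Study 2.

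**The concern.** Matching makes the two groups alike on the matched variables, so their contribution mostly cancels from the PF-minus-control difference. An ANOVA without those variables still counts that contribution as noise. Where the variables matter for the outcome, the computed standard error exceeds the true one, the test rejects less often than 5% under the null, and part of the efficiency gained by matching is given away.

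The stake is efficiency in an observational comparison: confidence intervals wider than needed for symptomatic side versus control, and a higher chance of missing a real difference in gait or segment motion. This mechanism does not bias the estimate.

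**Working it through.** **Inputs.** From the documents: four matching variables, three categories (two of them from the same PF participants), two trials per person, alpha 0.05 (taken as two-sided). Assumed, because the documents are silent: outcome SD 1, 20 or 30 per group, true difference 0.6 SD, matching variables explaining R² = 0 to 30% of outcome variance, and a correlation w = 0.7 between a person's two sides. There is no figure in the plan to reproduce.

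**Step 1: symptomatic side versus control, one value per participant.** With close matching,

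- SE used by the ANOVA: sqrt(2/n)
- true SE: sqrt(2(1 − R²)/n)
- ratio: 1/sqrt(1 − R²) = 1.05, 1.12, 1.20 for R² = 10, 20, 30%

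The large-sample type I error is 2[1 − Φ(1.96 × ratio)] = 3.9%, 2.8%, 1.9%.

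**Step 2: power for 0.6 SD, normal approximation.** Write s = sqrt(2/n), which is 0.316 at n = 20 and 0.258 at n = 30.

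- without the covariates: Φ[(0.6 − 1.96s)/(s·sqrt(1 − R²))]
- with them: Φ[0.6/(s·sqrt(1 − R²)) − 1.96]

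| n per group | R² | without | with | gain (points) |
|---|---|---|---|---|
| 20 | 0% | 0.475 | 0.475 | 0 |
| 20 | 10% | 0.474 | 0.516 | 4 |
| 20 | 20% | 0.472 | 0.564 | 9 |
| 20 | 30% | 0.470 | 0.621 | 15 |
| 30 | 0% | 0.642 | 0.642 | 0 |
| 30 | 10% | 0.649 | 0.688 | 4 |
| 30 | 20% | 0.658 | 0.738 | 8 |
| 30 | 30% | 0.668 | 0.793 | 13 |

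**Step 3: simulation.** Simulating the three-category ANOVA with individual matching and w = 0.7 gives type I error of about 4 to 5%, 3% and 2 to 3% at R² = 10, 20 and 30%. Adding the covariates brings this contrast back to about 5% and adds 4 to 16 points of power. A two-group simulation with matching of group means only (n = 30) gives type I error of 4.1, 3.2 and 2.4%, and power of 0.65, 0.65, 0.64 without covariates against 0.69, 0.74, 0.77 with them. The effect therefore does not need individual pairs. At R² = 0 and n = 20 the covariates cost under one point of power (0.453 against 0.448 with individual matching, 0.472 against 0.468 with group matching).

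**Step 4: where the direction reverses.** Let r be the correlation that matching induces between a patient and a control.

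- *Mean of both PF sides versus control, sides treated as independent.* ANOVA variance is (1/4 + 1/4 + 1)/n = 1.5/n. The true variance is [(1 + w)/2 + 1 − 2r]/n. The ANOVA SE is too small unless r > w/4, which at w = 0.7 is r > 0.175. The SE ratio is sqrt(1.5/1.85) = 0.90 at r = 0, sqrt(1.5/1.65) = 0.95 at r = 0.1 and sqrt(1.5/1.45) = 1.02 at r = 0.2. Type I error is about 0.08, 0.06 and 0.05.
- *Two trials entered as separate rows, symptomatic side versus control.* With between-trial correlation t, the ratio is sqrt(1/(1 + t − 2r)), too small unless r > t/2. At t = 0.9 it is 0.73 at r = 0 and 0.82 at r = 0.2.

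**Step 5: covariates alone are not enough.** In the three-category simulation, adding the four covariates while still treating the two sides as independent moved type I error for the mean of PF sides versus control from about 3 to 7% up to about 7 to 9% at R² = 10 to 30%. The ignored matching had been offsetting the ignored side-to-side dependence; removing only the first exposes the second. A person-level adjusted analysis held about 5%.

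**The case against.** A reader might infer that the PF-versus-control standard errors are simply too large, that the true type I error is below 5%, and that real differences are being missed. The documents do not support this. They give no explained variance, and if the four variables do not predict the outcome the effect is nil. Nor does the direction hold for every contrast: Step 4 shows it can reverse when sides or trials of one person are treated as independent. The within-person structure is at least as clear a dependence in the plan as the matching. All of this stands, and it limits the point to one contrast and to variables that are prognostic.

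A reader might also infer that a paired analysis is required. The wording and the demographic check fit group-level balancing at least as well as individual pairing. Pairing has its own cost: at r = 0, n = 20 and a 0.8 SD difference, power is 0.67 paired against about 0.70 for the ANOVA. This stands too, but covariate adjustment needs no pairs.

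Third, a plain one-way ANOVA is inferred from silence in a short summary. Study 3 does specify a repeated measures ANOVA, which makes the plain reading of Study 1 more likely but does not prove it. What survives under any reading is that no term for the matching variables is stated.

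Finally, covariate adjustment in a small study is sometimes resisted as costly. With 20 per group and nothing explained, the cost is under one point of power, so this does not carry weight.

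**Conclusion.** The point holds conditionally. Study 1 builds four variables into its design and names none of them in its main analysis. So far as they predict gait and foot motion, the symptomatic-side-versus-control comparison is conservative: type I error about 2 to 5% and about 4 to 16 points of power forgone, assuming 20 to 30 per group, a 0.6 SD difference, 10 to 30% of variance explained and one value per participant. At 0% explained there is no loss to speak of. None of these assumptions can be checked against the documents.

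The broader statement that all PF-versus-control standard errors are inflated cannot be made, because the handling of the two sides and two trials is unstated and can push other contrasts towards too many false positives. This is a cheap improvement, not a flaw that invalidates the comparison.

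**What to change.** Specify a linear mixed model for the three categories with age, gender, height and weight as covariates and a random participant effect. State whether the two trials are averaged or nested within participant and side. State whether matching was individual or group-level, and add a matched-set effect only if controls were individually paired. Report the unadjusted comparison as secondary.

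Do not add the covariates to an ANOVA that treats the two PF sides as independent (Step 5).

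Cost: a few sentences in the SAP, or a re-run if the analysis is already done; four degrees of freedom; slightly more analysis work. The four variables were already used for matching, so no new data are needed.

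### Study 1 puts both feet of the same patients into an ANOVA with no participant term; if it is an ordinary ANOVA and the feet are positively correlated, the side comparison loses power

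*Combined protocol and SAP*

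**What the plan says.** In Study 1's Study Protocol, the aim is to compare patients with controls: "This study was designed to compare multisegment foot motion and gait between individuals with PF and healthy controls". Its Statistical Analysis Plan then states that "the main analysis investigated how foot movements and gait differed among three categories", namely "the symptomatic side of individuals with PF, the asymptomatic side of individuals with PF, and healthy controls. This comparison was done using ANOVA". The significance level is 0.05. No type of ANOVA, participant effect or follow-up contrast is named.

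The only matching described is between patients and controls: "The two groups were matched by age, gender, height, and weight". Whether this was one-to-one or at group level is not stated. It does not concern the two feet of one patient.

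On the data that enter the analysis, "the two successive trials, with gait speed similar to the controls, were selected for detailed analysis". The text does not say whether the two trials are averaged, or whether a control contributes one foot or both. No sample size, SD or between-foot correlation is given.

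Study 3's Statistical Analysis Plan, in the same document, does name a within-person method: "Outcome measures were analyzed using two-way repeated measures ANOVA to examine".

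**The concern.** The symptomatic and asymptomatic categories come from the same patients; only the controls are separate people. An ordinary ANOVA treats all three categories as independent samples. It therefore uses the wrong error term for the comparison in which each patient serves as their own control.

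Although the stated aim is patients versus controls, the plan places both sides in the main analysis, so the side difference is part of it. If the feet are positively correlated, a real side difference becomes easier to miss, and a non-significant result could be read as showing that the two feet move alike. The same omission can also disturb comparisons with controls, in a direction that depends on how the control feet are entered.

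**Working it through.** There is no stated figure to reproduce. All inputs below are assumptions: 20 patients, 20 controls, equal SDs (s), normal data, one value per foot (n values per category), two-sided 5% tests, and between-foot correlation rho from 0 to 0.8. Power is for a 0.5 SD shift of the symptomatic side only. Size and power come from simulation (40,000 datasets per setting) unless a formula is shown.

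**1. Side contrast.** An ordinary ANOVA takes the variance of the side difference as 2s²/n. The true variance is 2s²(1-rho)/n. The standard error is therefore too large by 1/sqrt(1-rho); at rho 0.5 this is 1/sqrt(0.5) = 1.41.

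- Large-sample size at rho 0.5: 2[1 - Phi(1.96/sqrt(0.5))] = 2[1 - Phi(2.77)] = 0.6%.
- Large-sample power of the ordinary contrast: Phi((ncp - 1.96)/sqrt(1-rho)), with ncp = 0.5·sqrt(20/2) = 1.58. At rho 0.5 this is Phi(-0.38/0.707) = 29.6%.
- Paired t power at rho 0.5: noncentral t with 19 df and noncentrality 0.5·sqrt(20)/sqrt(2·0.5) = 2.24, giving 56.5%.

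| rho | SE ratio | Size, ordinary | Power, ordinary | Power, paired |
|---|---|---|---|---|
| 0 | 1.00 | 5.1% | 34% | 32% |
| 0.1 | 1.05 | 4.0% | 34% | 35% |
| 0.3 | 1.20 | 2.0% | 32% | 43% |
| 0.5 | 1.41 | 0.6% | 29% | 56% |
| 0.8 | 2.24 | <0.1% | 21% | 92% |

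For 15 to 30 patients, the change in power from pairing is about -2 points at rho 0, 1 to 3 at 0.1, 10 to 13 at 0.3, 24 to 28 at 0.5 and 53 to 71 at 0.8.

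**2. Other tests, one value per control.** The overall F test has size 3.8/3.6/3.4% at rho 0.3/0.5/0.8, so it is mildly conservative. One PF side against unmatched controls keeps its size (4.9 to 5.2%). For the mean of both PF feet against controls, the true variance is s²(1+rho)/(2n) + s²/n = (1.5s²/n)(1 + rho/3), while the ANOVA assumes 1.5s²/n. Size at rho 0.5 is 2[1 - Phi(1.96/sqrt(1.167))] = 7.0%, which is mildly liberal.

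**3. Other tests, both control feet entered as separate values** (same rho in controls). The side contrast is still conservative, but the rest changes direction. The overall F test has size of about 5.5/6.0/7.6% at rho 0.3/0.5/0.8, and one PF side against controls about 6.2/7.0/8.5%. For that second contrast the true variance is s²/n + s²(1+rho)/(2n), again 1 + rho/3 times the assumed 1.5s²/n.

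**4. Trials entered separately.** If the two trials are not averaged (assumed between-trial correlation 0.8, one foot per control, between-foot correlation 0.3 before trial noise), side-contrast size is about 9% and overall F size about 17%. The conservatism in step 1 therefore requires one value per foot.

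**The case against.** The strongest objection is that the document is a short summary, and the word ANOVA does not rule out a repeated-measures form. That stands. The ordinary reading is supported by the contrast with Study 3, which names repeated measures, but it remains an inference.

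Second, every magnitude is assumed. That also stands. Only the direction for the side contrast is firm, and only for positive rho with one value per foot. At rho 0 nothing is lost and the paired test is about 2 points weaker.

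Third, the stated aim is patients versus controls. The three-category comparison is nevertheless the main analysis. The aim does limit the benefit: if both PF feet shift by the same 0.5 SD, the mixed model does not help the overall test.

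A reader might infer that the analysis is conservative throughout, so that no false positives can arise. The documents do not support this. It needs one value per control and one value per foot, neither of which is stated, and even then the mean of both PF feet against controls is liberal. The opposite inference, that the false-positive rate is definitely inflated, is not supported either, for the same reason.

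**Conclusion.** The concern holds conditionally and should be fixed. As written, the main analysis of Study 1 has no term for two feet from one patient. If it is an ordinary ANOVA, the feet are positively correlated and each foot gives one value, the side contrast is conservative and loses power: about 29% against 56% under the assumed n = 20, 0.5 SD and rho 0.5.

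For the remaining tests the direction is open. With one value per control, at rho 0.5, the overall F test is mildly conservative (about 3.5%), one PF side against unmatched controls keeps its size, and the mean of both PF feet against controls is mildly liberal (about 7%). With both control feet as separate values, the F test (about 6%) and one PF side against controls (about 7%) are liberal.

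The documents do not show that the pairing was in fact ignored, nor that any Study 1 conclusion is wrong. Confidence is medium.

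**What to change.** State the type of ANOVA, the number of feet per control and how the two trials enter. Unless the pairing was already modelled:

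- Fit a linear mixed model with limb category (symptomatic, asymptomatic, control) as fixed effect, participant as random intercept and Kenward-Roger degrees of freedom. Enter one value per foot, the mean of the two selected trials.
- Report the three pairwise contrasts with Holm adjustment.
- If a paired test for the two sides plus independent tests against controls is preferred, enter one value per control: one pre-specified foot, or the mean of both feet. Independent tests do not otherwise handle two feet per control.
- Limit the paired side contrast to patients with one symptomatic and one asymptomatic foot. The eligibility text ("Participants included people who had been experiencing foot pain related to PF for at least one month") does not say that bilateral disease was excluded.

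The cost is a re-run on existing data with standard software. In the same n = 20 setting the statistical downsides are small. The paired test loses about 2 points of side-contrast power if rho is near 0 (34% to 32%). The mixed-model side contrast is slightly liberal at rho 0 (5.8%). The overall test loses about 3 points of power if both PF feet shift equally (27.7% against 30.3% for the ordinary ANOVA at rho 0.5; 26.0% against 29.2% at 0.8).

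### Study 2 states no stability criterion or change question for the one-week retest, so if foot problems change unequally over that week the ICC will understate the reliability of the FFI-Th

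*Combined protocol and SAP*

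**What the plan says.** The Study 2 Statistical Analysis Plan gives the test-retest method in one clause: "Test-retest reliability was measured by the intraclass correlation coefficient (ICC) from repeated assessments one week apart". The result is then graded against fixed bands, "with ICC values interpreted as poor (<0.5), moderate (0.5–0.75), good (0.75–0.9), or excellent (>0.9".

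The Study 2 Study Protocol describes the population in one sentence: "Participants included adults who could read and understand Thai and reported foot problems". It sets no minimum symptom duration, whereas Study 1 asks for at least one month of pain in its plantar fasciitis group. The sample size is given as "A minimum sample size of 48 participants was determined based on prior reliability studies of similar FFI versions". The pain-VAS and EQ-5D-5L are collected, but the plan does not say that either is repeated at the retest.

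Four things are not stated:
- any requirement, or any check, that the foot problem was unchanged between the two assessments;
- whether treatment during the week is recorded;
- whether all participants or a subset were retested;
- whether the ICC measures consistency or absolute agreement.

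**The concern.** Test-retest reliability asks how far two scores agree when the person has not changed. With only two assessments per person, the ICC cannot separate instrument error from real change: a participant who improved and a participant who answered inconsistently both enlarge the within-person variance. People selected because they report a foot problem, with no minimum duration, may include some whose problem is resolving or worsening.

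The plan turns the ICC into a label with boundaries at 0.5, 0.75 and 0.9. An instrument that deserves the top label could be reported one band lower. A larger sample would not cure this, because the distortion is in the quantity being estimated and not in its sampling error.

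**Working it through.** **The plan's own figure.** The only planning number is the minimum of 48. No expected ICC, null value, power or precision is given, so it cannot be reproduced. It does not enter the bias calculation.

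**Inputs.** From the documents: two assessments, one week apart, and the bands at 0.5, 0.75 and 0.9. Assumed, because the documents give nothing: true reliability R; a share p of participants who improve; and an improvement D in units of the total-score SD, unrelated to the starting score.

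**Model.** First score X1 = T + e1 and second score X2 = T − D·B + e2, with var(T) = R, var(e) = 1 − R, and B equal to 1 with probability p, otherwise 0.
- The covariance of the two scores is R.
- Their variances are 1 and 1 + p(1−p)D², with mean 1 + p(1−p)D²/2.
- The mean shift pD adds (pD)²/2 to the denominator for absolute agreement.

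Hence:
- Consistency ICC = R / (1 + p(1−p)D²/2)
- Absolute-agreement ICC = R / (1 + p(1−p)D²/2 + p²D²/2) = R / (1 + pD²/2)

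**Results for R = 0.92.**

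| p | D | Absolute agreement | Consistency |
|---|---|---|---|
| 0 | – | 0.920 | 0.920 |
| 0.2 | 0.5 | 0.92/1.025 = 0.898 | 0.92/1.020 = 0.902 |
| 0.3 | 0.5 | 0.92/1.0375 = 0.887 | 0.92/1.02625 = 0.896 |
| 0.2 | 1 | 0.92/1.10 = 0.836 | 0.92/1.08 = 0.852 |
| 0.3 | 1 | 0.92/1.15 = 0.800 | 0.92/1.105 = 0.833 |

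A simulation with 400,000 participants per case agreed with every row that has change to within 0.001.

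**A second model.** Let every participant change by a random amount with SD c, in true-score SDs, centred on zero and independent of the starting value. The ICC is then 1/(1 + (1−R)/R + c²/2). If the total variance is instead held constant, it is R(1 − c²/2).
- R = 0.95, c = 0.4: 0.883 and 0.874 (excellent becomes good).
- R = 0.90, c = 0.2: 0.884 and 0.882. At c = 0.5: 0.809 and 0.787.
- R = 0.80, c = 0.5: 0.727 and 0.700 (good becomes moderate).

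**Where the effect is absent or reversed.** If everyone shifts by the same amount, the consistency ICC stays at R and only absolute agreement falls: with R = 0.90 and a shift of 0.5 true-score SD, 1/(1 + 0.1/0.9 + 0.125) = 0.809. If true scores spread in proportion to their starting value by a factor of 1.1, the ICC is 1.1/((1 + 1.21)/2 + 0.1/0.9) = 0.905 against 0.90, slightly higher.

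**Scale.** For a true ICC of 0.90, simulated 95% sampling limits at n = 48 are about 0.83 to 0.94.

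**The case against.** A reader might infer that the ICC was computed in everyone with a foot problem and is therefore biased downward. The documents support neither step. They do not say who was retested, and they are a protocol summary, so what can be said is that no criterion is stated. Bias needs real and unequal change within the week. No figure in the documents shows such change, Study 2 is described as cross-sectional, and no treatment is planned in it. The absence of planned treatment does not show that none was taken, but it gives no rate either.

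The upper cases are severe: nothing in the documents supports 30% of participants improving by a full SD in seven days. The mildest case crosses 0.9 by only 0.002 for absolute agreement and does not cross it for consistency. Starting from 0.90, which is already in the good band, the same four combinations give 0.78 to 0.88 for absolute agreement and the label does not move. The 0.5 SD losses, about 0.02 to 0.03, are small beside the sampling limits at n = 48. The bands are descriptive, any error of this kind would normally understate reliability, and Study 3 as described measures pain VAS and gait parameters and not the FFI-Th.

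All of that stands, and it limits the point to a conditional one of modest consequence. It does not remove it: the plan offers no means of telling patient change from instrument error, and test-retest reliability is a main result of a validation study.

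One further objection bears on the remedy. The answer that nothing has changed is given at the same sitting as the retest, so it may share error with the retest score. Suppose no true change, a correlation of 0.5 between the change rating and the observed score difference, and exclusion of the 20% to 40% who rate themselves most changed. A true 0.88 then becomes about 0.90, and a true 0.90 becomes 0.91 to 0.92. This also stands, and it rules out relying on the stable-group ICC alone.

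**Conclusion.** The point holds conditionally. Study 2 states no stability criterion and no change question for its one-week retest. If foot problems change by different amounts, in a way not tied to the starting score, the ICC understates reliability. From a true 0.92, the assumed range runs from 0.90 (20% improving by 0.5 SD, either ICC form) to 0.80 for absolute agreement or 0.83 for consistency (30% improving by 1 SD). With no change the bias is zero. Every share and amount of change here is an assumption. The documents do not establish that the ICC is biased, or by how much. This is a cheap improvement to the plan and not a flaw that invalidates the validation study.

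**What to change.** Add one self-completed question to the retest form: *Compared with last week, is your foot problem better, the same or worse?* In the Study 2 analysis plan, name the ICC form, say who is retested, and report the ICC with its 95% interval twice, with equal prominence: in those answering *the same* and in all retested participants. Neither should be demoted, because the two can err in opposite directions.

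The cost is one question and a sentence or two in the plan. The stable-group interval is somewhat wider: at an ICC of 0.90, by the Fisher-z approximation, about 0.83 to 0.94 with 48 participants becomes 0.81 to 0.95 with 34 (assuming 30% are excluded: 48 × 0.7 ≈ 34). The other cost is the slight flattering of the stable-group ICC described above.

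The analysis plan is written in the past tense, so retesting may already be complete. In that case, use the pain-VAS to define stability if it was repeated at the retest. Otherwise report the ICC in all retested participants and state the limitation.
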